5.3 Randomization and Blinding

In total, 352 subjects will be randomized to 1 of 8 treatment groups in an equal ratio. Randomization will be used to avoid bias in the assignment of subjects to treatment, to increase the likelihood that known and unknown subject attributes (eg, demographic and baseline characteristics) are evenly balanced across treatment arms, and to enhance the validity of statistical comparisons across treatment arms.

Subjects and study personnel will be blinded to the treatment (placebo or ESN364), dosage (30 mg, 60 mg, etc.), and dosing regimen (QD or BID).

Randomization will be based on a computer-generated randomization schedule prepared by Medpace, Inc. Biostatistics using SAS® software (SAS Institute Inc., Cary, NC, USA) prior to the start of the study. The randomization will be balanced using randomly permuted blocks across the treatment arms. The randomization list will be retained by Medpace Biostatistics until the end of the study (database lock). A copy will be sent in a sealed envelope to the bioanalytical laboratory responsible for plasma drug and serum hormone determination before the start of the study as applicable. Because of a planned early timepoint analysis (see Section 10.2.3) and because PK/PD modeling will start prior to database hard-lock, specific assigned Sponsor staff involved in these activities (or delegates, if outsourced to an external vendor) will be unblinded after recruitment has been completed. Details of the unblinding will be documented in a separate charter to ensure the direct study team remains blinded and that unblinded results are restricted to a very small group independent of the study team.

Subjects will be assigned a randomization number from the Interactive Response Technology (IRT) system upon enrollment. The randomization list will be uploaded into the IRT system. Based on this randomization list, the study drug will be packaged and labeled. Medication numbers will be preprinted on the study drug labels. The study team, including those involved in data management, clinical, medical, or statistical review of the study data, will also be blinded during the study as they will not have access to the randomization list. Medpace, the Contract Research Organization (CRO) performing data management and statistical activities, will receive a copy of the randomization list at database lock. The study drug administered to a subject can be identified by the IRT system. The IRT system will allow rapid access to the treatment allocation codes when relevant for site or CRO personnel.

5.4 Breaking the Blind

The randomization list will not be available to the Investigator or other employees of the study site, subjects, monitors, or blinded Medpace and Sponsor personnel before unblinding of the data, unless in case of emergency. Blinding will be maintained unless unblinding is considered mandatory because of a life-threatening situation for management of medical treatment. In such case, the date at which breaking of the code occurs, the person who breaks the code, and the reason why the code is broken will need to be documented in the subject's file. Sites will use IRT to break the blind. The Medpace IRT team will supply a passcode (6 digits) in a sealed envelope for each site in order to break the blind in the IRT system. Site personnel should inform the Medical Monitor immediately. If the Investigator accidentally breaks the code, the Medical Monitor and the Clinical Trial Manager must be also informed as soon as possible. If the code is broken by the Investigator or by someone of his/her clinical staff, the subject must be withdrawn from the study and must be

followed as appropriate. If the code is broken by the Sponsor or designee for safety reporting purposes or the planned early timepoint analysis, the subject may remain in the study.

Because of a planned early timepoint analysis (see Section 10.2.3) and because PK/PD modeling will start prior to database hard-lock, specific assigned Sponsor staff involved in these activities (or delegates, if outsourced to an external vendor) will be unblinded after recruitment has been completed. Details of the unblinding will be documented in a separate charter to ensure the direct study team remains blinded and that unblinded results are restricted to a very small group independent of the study team.

5.5 Drug Supplies

5.5.1 Formulation and Packaging

ESN364 and placebo will be manufactured, packaged, and labeled under the responsibility of Ogeda S.A. The study drug and placebo are manufactured under current Good Manufacturing Practice (GMP), as required by the current Good Clinical Practice (GCP), at Pharmavize N.V. (Mariakerke, Belgium). The packaging and labeling of study drug will be in accordance with applicable local regulatory requirements.

The ESN364 and placebo capsules will be packaged in high-density polyethylene bottles with polypropylene closure. Subjects will be assigned 2 bottles as a kit (1 bottle labeled “morning” and 1 bottle labeled “evening”) at Day 1 (Visit 2), Week 4 (Visit 3), and Week 8 (Visit 4). Each bottle will contain 34 capsules of ESN364 or placebo.

Labels will be printed in the local language of the countries in which the study takes place in accordance with applicable local regulations and will contain the following:

- Protocol number;
- Medication number;
- Visit number;
- Batch number;
- Storage conditions;
- Contents;
- The statements “Keep out of reach and sight of children,” “For oral route only,” and “For clinical study use only”; and
- Sponsor (or sponsor representative) name.

ESN364 will be supplied as immediate-release Coni cap size 0 white opaque hard gelatin capsules for oral administration in active dosage strength ranges of 15 mg to 180 mg. Capsules will be prepared according to the dosing scheme in Table 1. A copy of the certificate of analysis will be provided to study sites. The qualitative composition of the ESN64 capsules is provided in Table 2.

Table 2. Qualitative Composition of ESN364 Hard Gelatin Capsules

Component	Function
ESN364	Active pharmaceutical ingredient
Starch, pregelatinized	Filler
Croscarmellose sodium	Disintegrant
Silicon dioxide	Glidant
Magnesiumstearate	Lubricant

Placebo will be supplied as hard gelatin capsules that are visually indistinguishable from the investigational product. The placebo capsules contain the same excipients as ESN364 and will be supplied in capsules shells identical to ESN364.

5.5.2 Study Drug Preparation and Dispensing

ESN364 and placebo are manufactured under current GMP, as required by the current GCP, at Pharmavize N.V. (Mariakerke, Belgium). Study drug will be assigned by the IRT to study sites/subjects.

5.5.3 Study Drug Administration

Subjects will be assigned 2 bottles of study drug as a kit (1 bottle labeled “morning” and 1 bottle labeled “evening”) at Day 1 (Visit 2), Week 4 (Visit 3), and Week 8 (Visit 4). Each bottle will contain 34 capsules of ESN364 or placebo. Study drug should be dispensed under the supervision of the Investigator, a qualified member of the clinical staff, or the hospital/clinic pharmacist.

All study visits should be conducted in the morning. Subjects should be fasted (defined as nothing by mouth except for water [up to 1 hour before study drug intake] for at least 10 hours prior to study visit). Day 1 (Visit 2) should be planned to allow for first intake of study drug (“morning” dose) at the study site between 7:00 AM and 10:00 AM. Following Day 1 (Visit 2), each subsequent visit should be planned at the same time of day (morning) for each subject.

Study drug intake will be done with a glass of room temperature tap water. The first intake of study drug will take place at the study site on Day 1 (Visit 2) between 7:00 AM and 10:00 AM under the supervision of the study staff. On study visit days (Day 1 [Visit 2], Week 4 [Visit 3], and Week 8 [Visit 4], only), the morning dose of study drug will be taken at the study site under the supervision of the study staff, after collection of predose blood samples. Subjects will be instructed to arrive at the study site fasted (defined as nothing by mouth except water [up to 1 hour prior to study drug intake] for at least 10 hours prior to study visit). On all other days throughout the treatment period, subjects will be instructed to take their morning dose of study drug at home, around the same time of the day and spaced as near to 12 hours apart as possible (preferably between 7:00 AM and 10:00 AM and 7:00 PM and 10:00 PM). Intake of study drug should be preferably 1 hour before or 2 hours after meals.

Subjects need to record all home study drug intake in the electronic Patient-Reported Outcome (ePRO) diary.

In the event a subject accidentally misses a scheduled dose of the study drug, the missed dose should be skipped and the subject should resume the usual dosing schedule.

Any deviation from the treatment regimen defined in the protocol must be documented in the eCRF.

5.5.4 Treatment Compliance

Subjects will be assigned 2 bottles of study drug as a kit (1 bottle labeled “morning” and 1 bottle labeled “evening”) at Day 1 (Visit 2), Week 4 (Visit 3), and Week 8 (Visit 4). Each bottle will contain 34 capsules of ESN364 or placebo.

On visit days during the treatment period (Day 1 [Visit 2], Week 4 [Visit 3], and Week 8 [Visit 4], only), the morning dose of study drug will be taken at the study site under the supervision of the clinical staff. All other study drug intakes (evening dose and morning dose on all days without visits) will take place at home. When taking study drug at home, subjects will be asked to record their home study drug intake in the ePRO diary. Subjects will also be asked to return all unused study drug.

Compliance of study drug intake will be assessed by counting returned study drug in addition to reviewing ePRO entries of study drug intake. Any discrepancies between returned study drug number and dosing in the ePRO diary will be discussed with the subject for whom a discrepancy was seen and recorded in the source documents and the eCRF. If a subject demonstrates continued non-compliance with study drug dosing ($\leq 85\%$ compliance) despite educational efforts, the Investigator should contact the Sponsor to discuss withdrawal of the subject from the study.

5.5.5 Storage and Accountability

The Investigator (or his/her designee) is responsible for the safe storage of all study drug assigned to the study site. Study drug will be stored in a locked, secure storage facility with access limited to those individuals authorized to dispense the study drug and maintained within the appropriate ranges of temperature. All study drug must be stored as specified at delivery and in the original packaging. Instructions for the subjects regarding the storage and handling of the study drug will also be provided to the study sites.

ESN364 must be stored at ambient conditions (15°C to 30°C or 59°F to 86°F), should not be exposed to freezing temperatures, and should be protected from light during storage at the study site. Study drug is stable up to 24 months at 25°C with 60% relative humidity.

Daily temperature logging of the study drug storage room at the study site should be performed. In the event a deviation in storage conditions should occur, the site must discontinue dispensing the affected study drug and notify the Clinical Research Associate (CRA). The same instruction applies for temperature deviations occurring during shipment of study drug to the sites.

The Investigator is responsible for ensuring that all study drug received at the study site is inventoried and accounted for throughout the study. As misallocations of study drug will have an impact on study execution and will jeopardize the validity of the data obtained, utmost care should be taken to correctly dispense the study drug as assigned by the randomization system.

Subjects will be assigned 2 bottles of study drug as a kit (1 bottle labeled “morning” and 1 bottle labeled “evening”) at Day 1 (Visit 2), Week 4 (Visit 3), and Week 8 (Visit 4). Each bottle will contain 34 capsules of ESN364 or placebo. Study drug should be dispensed under the supervision of the Investigator, a qualified member of the clinical staff, or the hospital/clinic pharmacist. The Investigator must maintain accurate records demonstrating date and amount of study drug supplied to whom and by whom. Study drug will be supplied only to subjects participating in the study.

The site monitor will periodically check the supplies of study drug held by the Investigator or pharmacist to ensure accountability and appropriate storage conditions of all study drug used.

Subjects must be instructed to return all unused study drug at Day 1 (Visit 2), Week 4 (Visit 3), Week 8 (Visit 4), and Week 12 (Visit 5)/ET. A record of any returned study drug will be kept for each subject. Returned study drug must not be relabeled or dispensed again.

Unused study drug and study drug returned by the subject (if applicable) must be available for verification by the site monitor during on-site monitoring visits. Any discrepancies between returned and expected returned study drug should be explained and documented.

After the last visit of the last subject in the study (Last Subject Last Visit), any unused study drug (including any study drug returned by the subject) will be returned to the Sponsor or designee.

5.6 Prior and Concomitant Medications and/or Procedures

5.6.1 Excluded Medications and/or Procedures

Current use of hormonal medications such as hormone therapy or hormonal contraception or any treatment for vasomotor symptoms (prescription, over the counter, or herbal) is not allowed during the study. Prescription medications for the treatment of vasomotor symptoms should be washed out after consultation with the prescribing physician and as per package insert guidance to ensure clinical safety. A minimum of 5 half-lives is required prior to screening. For women who recently discontinued hormone therapy, the therapy must have been discontinued for at least the following durations prior to the screening visit:

- 1 week or longer for prior vaginal hormonal products (rings, creams, gels, inserts);
- 4 weeks or longer for prior transdermal estrogen alone or estrogen/progestin products;
- 8 weeks or longer for prior oral estrogen and/or progestin therapy;
- 8 weeks or longer for prior intrauterine progestin therapy;
- 3 months or longer for prior progestin implants and estrogen alone injectable drug therapy; or
- 6 months or longer for prior estrogen pellet therapy or progestin injectable drug therapy.

5.6.2 Restricted Medications and/or Procedures

Any medications, other than those excluded by the protocol (see Section 5.6.1), that are considered necessary for a subject's welfare or will not interfere with the study drug may be given at the discretion of the Investigator.

Analgesics are permitted on an as-needed basis. Long-term or prophylactic use is allowed if stable for >3 months.

The use of stable doses (defined as no relevant dose changes within 3 months prior to screening) of thyroid replacement therapy is allowed.

The use of stable doses (defined as no relevant dose changes within 3 months prior to screening) of antihypertensive medication (except clonidine) is allowed on the condition that hypertension is well controlled.

The use of stable doses (defined as no relevant dose changes within 3 months prior to screening) of antidepressants is allowed.

Occasional use (defined as less than 3 times per week) of benzodiazepine or Z-drugs can be allowed on an as-needed basis.

Restricted use (≤ 7 days) of topically applied corticosteroid containing cream/ointments is allowed.

Active prescription for opiates is allowed at the discretion of the Investigator.

The Sponsor or designee must be notified in advance (or as soon as possible thereafter) of any instances in which prohibited therapies are administered.

For any medication for which the Investigator is uncertain if it might interfere with the screening assessments or study drug, the Medical Monitor should be consulted.

5.6.3 Documentation of Prior and Concomitant Medication Use

All therapies (prescriptions, over the counter, and herbal), other than the study drug, administered from informed consent until the last study-related activity must be recorded in the source documents and in the concomitant therapy section of the eCRF (name of the drug, dosage, route, and dates of administration). If a concomitant medication is started later than 2 weeks after the last intake of study drug, it will only be recorded when linked to an adverse event.

In the event of observed liver enzyme elevations during the study, additional therapies will be recorded. All therapies (prescriptions, over the counter, and herbal) administered from 90 days prior to informed consent up to informed consent will be recorded in the source documents and in the concomitant therapy section of the eCRF (name of the drug, dosage, route, and dates of administration).

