- z. Includes compliance of study drug intake and ePRO completion. Subjects will be asked to return all unused study drug. Compliance of study drug intake will be assessed by counting returned study drug in addition to reviewing ePRO entries of study drug intake. Any discrepancies between returned study drug number and dosing in the ePRO diary will be discussed with the subject for whom a discrepancy was seen and recorded in the source documents and the eCRF.
- aa. Adverse events and intake of concomitant medication(s) will be monitored continuously from informed consent until the last study-related activity.

BALP = bone alkaline phosphatase; C-SSRS = Columbia Suicide Severity Rating Scale; CTX = carboxy-terminal telopeptide of type I collagen; CCI
[REDACTED]; E2 = estradiol; ECG = electrocardiogram; eCRF = electronic Case Report Form; ET = early termination; ePRO = electronic Patient-Reported Outcome; FSH = follicle-stimulating hormone; GCS = Greene Climacteric Scale; HBsAG = hepatitis B virus surface antigen; HCV = hepatitis C virus; HFRDIS = Hot Flash Related Daily Interference Scale; HIV = human immunodeficiency virus; LH = luteinizing hormone; LSEQ = Leeds Sleep Evaluation Questionnaire; MENQoL = Menopause-Specific Quality of Life; P1NP = procollagen type 1 amino-terminal propeptide; PD = pharmacodynamic; PGX = pharmacogenomic; PK = pharmacokinetic; SHBG = sex hormone-binding globulin.

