6.4 Other Variables

Duration of treatment exposure

Duration of exposure to treatment will be calculated in days, using the following formula:

$$\text{Days of exposure} = \text{date of last dose} - \text{date of first dose} + 1$$

Study drug compliance

Study drug compliance will be calculated using the following formula:

$$\text{Study drug compliance} = 100 \times \frac{\text{actual capsules consumed}}{\text{expected capsules consumed}}$$

where

$$\text{Actual capsules consumed} = \text{total capsules dispensed} - \text{total capsules returned}$$

$$\text{Expected capsules consumed} = (\text{last dose date} - \text{first dose date} + 1) \times 2 \text{ capsules per day}$$

Study drug compliance of morning dose

Study drug compliance of morning dose will be calculated using the following formula:

$$\text{Compliance of morning dose} = 100 \times \frac{\text{actual capsules consumed}}{\text{expected capsules consumed}}$$

where

Actual capsules consumed = morning capsules dispensed – morning capsules returned

Expected capsules consumed = (last dose date – first dose date +1) capsules per day

Study drug compliance of evening dose

Study drug compliance of evening dose will be calculated using the following formula:

$$\text{Compliance of evening dose} = 100 \times \frac{\text{actual capsules consumed}}{\text{expected capsules consumed}}$$

where

Actual capsules consumed = evening capsules dispensed – evening capsules returned

Expected capsules consumed = (last dose date – first dose date +1) capsules per day

Diary interaction compliance during the treatment period

Diary compliance during the treatment period will be calculated using the following formula:

$$\text{Diary interaction compliance} = 100 \times \frac{\text{actual diary days with data recorded}}{\text{expected diary days with data recorded}}$$

where

Actual diary days with data recorded = number of diary days with any morning or evening dose or hot flash data recorded from Visit 2 up to and including the last day of exposure to treatment

Expected diary days with data recorded = date of last dose – date of Visit 2 + 1

Previous and concomitant medication

Previous medication is defined as medication with at least one dose taken before the date of the first dose of study drug.

Concomitant medication is defined as medication with at least one dose taken between the date of first dose (inclusive) and the date of last dose (inclusive) of study drug.

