7.2.4 Previous and Concomitant Medications

Previous medications are coded with WHO-DD, and will be summarized by anatomic main group (ATC 1st level), therapeutic subgroup (ATC 2nd level), chemical subgroup (ATC 4th level), and preferred WHO name by treatment group for the SAF.

As with previous medications, concomitant medications will be summarized for each treatment group by anatomic main group (ATC 1st level), therapeutic subgroup (ATC 2nd level) and chemical subgroup (ATC 4th level) and preferred WHO name for the SAF. Subjects taking the same medication multiple times will be counted once per medication and investigational period. A medication which can be classified into several chemical and/or therapeutic subgroups is presented in all chemical and therapeutic subgroups.

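### Medicines stopped before consent are recorded only after a liver enzyme elevation, so the by-arm previous-medication table will carry a small artefact if elevations differ by arm

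*Protocol*

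**What the plan says.** Protocol 5.6.3 sets one recording window for everyone: therapies "administered from informed consent until the last study-related activity must be recorded in the source documents". The next paragraph opens with a trigger: "In the event of observed liver enzyme elevations during the study, additional therapies will be recorded". The sentence after it says what is added, namely therapies "administered from 90 days prior to informed consent up to informed consent will be recorded in the source documents". These are entered "in the concomitant therapy section of the eCRF", where the routine records also go. The section gives no threshold for an elevation and describes no flag or separate form for the added records.

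Footnote aa of the schedule in Protocol Appendix A gives the same routine window: "intake of concomitant medication(s) will be monitored continuously from informed consent until the last study-related activity". No other provision in the documents collects pre-consent medication from all women.

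SAP 6.4 states: "Previous medication is defined as medication with at least one dose taken before the date of the first dose of study drug". It sets no earliest date. SAP 7.2.4 continues: "Previous medications are coded with WHO-DD, and will be summarized by anatomic main group", then by finer ATC levels and preferred name, by treatment group on the Safety Analysis Set. It has no exclusion or footnote for liver-triggered records, and SAP section 8 lists no change on this point.

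**The concern.** A previous-medication table is normally read as a baseline description, in which randomisation makes any arm difference a matter of chance. Here part of its content depends on something that happens after randomisation and that may depend on treatment. A woman who stopped a medicine shortly before consent appears in the table for that medicine if her liver enzymes later rise, and otherwise does not.

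What is at stake is interpretation of liver safety. ALT or AST above 3 x ULN is an adverse event of special interest (Protocol 9.15). Appendix D lists prior and concomitant medication among the confounders to weigh in a possible liver injury. If an arm has more elevations, the table would lean towards showing more prior medication in that same arm. That could be mistaken for a baseline imbalance that helps to explain the elevations.

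**Working it through.** The plan states no figure on this point, so there is none to reproduce. The check has two parts.

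**1. Which records are affected**

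| When the medicine was taken | Recorded for | In the SAP 6.4 definition? |
|---|---|---|
| Between consent and first dose, including medicines ongoing at consent | All women | Yes |
| Stopped within the 90 days before consent | Women with a liver enzyme elevation during the study | Yes |
| Stopped more than 90 days before consent | Not called for by 5.6.3 | Yes, but no data expected |

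Only the second row depends on outcome.

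**2. Size**

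Inputs:
- n = 44 per arm, planned (Protocol 10.2.4; SAP 4).
- q = true share of women with a medicine stopped in the 90 days before consent who are not otherwise counted. It is the same in every arm in expectation, and is taken to be the same among women who later have an elevation. Not in the documents; assumed 20% to 60%.
- e = share of an arm with a liver enzyme elevation. Not in the documents; assumed 0% to 5% on placebo and 0% to 20% on active.

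Formulas:
- Share of an arm entering the table through the look-back = q x e.
- Artefactual arm difference = q x (e_active - e_placebo), or 44 times that in women.

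| q | e placebo | e active | Placebo share | Active share | Difference | Women of 44 |
|---|---|---|---|---|---|---|
| 20% | 2% | 5% | 0.4% | 1.0% | 0.6 points | 0.26 |
| 40% | 5% | 5% | 2.0% | 2.0% | 0 | 0 |
| 40% | 2% | 10% | 0.8% | 4.0% | 3.2 points | 1.41 |
| 40% | 2% | 20% | 0.8% | 8.0% | 7.2 points | 3.17 |
| 60% | 2% | 20% | 1.2% | 12.0% | 10.8 points | 4.75 |
| 60% | 0% | 20% | 0.0% | 12.0% | 12.0 points | 5.28 |

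The true difference is zero in every row. The artefact vanishes when elevation rates are equal.

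**Dilution.** SAP 7.2.4 has no row for medicines stopped before consent. The extra records fall into drug-class and drug-name rows that also hold medicines recorded for everyone. Take assumed elevations of 1 of 44 on placebo and 5 of 44 on active, with q = 40%. The look-back adds 1 x 0.4 = 0.4 women and 5 x 0.4 = 2.0 women, a difference of 1.6. Suppose 13 of 44 in each arm are already in a class row (assumed), and all the extra women fall in that row and are not yet counted. The row then reads 13.4/44 = 30% against 15.0/44 = 34%, a ratio of 15.0/13.4, or about 1.1. A row for a drug that few women take after consent would be diluted less.

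**After the fix.** With one look-back for all women, the expected difference from this source is 0 for every q and e.

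**The case against.** **The 90-day sentence might apply to everyone.** Read alone, it could. But it directly follows the liver trigger, and if it were unconditional the promised additional therapies would have no content. The Appendix A footnote also starts at consent. The conditional reading is the natural one.

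**No imbalance is certain.** This stands. Without an arm difference in elevations, the result is patchy capture and not systematic imbalance. The documents give no elevation rates.

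**A reader might infer a large distortion.** With elevations in 1 of 44 and 5 of 44, the look-back records alone differ fivefold between arms. The documents do not support that as a description of the table, because the ratio isolates a subset that no row shows. The same example is 0.4 against 2.0 women, mixed with medicines recorded for all.

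**Liver causality is not judged from this table.** Largely right. Appendix D assesses cases individually, with medication history, confounders and sponsor narratives. SAP 7.5.2.1 tabulates liver criteria by arm and lists suspected cases of drug-induced liver injury. This limits the harm but does not make the table correct.

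**A reader might also infer that washed-out hormone or hot-flash therapy goes unrecorded.** Protocol 5.6.1 says "the therapy must have been discontinued for at least the following durations prior to the screening visit", and Protocol 6.2 collects consent forms at the screening visit. But exclusion criterion 1 refers to willingness to wash out, which suggests that some washouts are prospective. Doses taken after consent are recorded for all. The text of Protocol 6.1 on consent is not available here, so the order of consent and washout cannot be settled. Eligibility is in any case checked at screening and Day 1, and protocol deviations are summarised (SAP 7.2.2). Collecting a longer hormone-therapy history would be a separate preference about data collection.

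**Conclusion.** The point holds as a minor, easily removed flaw. The protocol's recording rule and the SAP's open-ended definition together make part of a baseline table depend on a post-randomisation outcome. Nothing in the SAP separates those records.

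The artefact is conditional on elevation rates differing by arm. Its size cannot be derived from the documents. Under the assumed ranges, unequal rates give an excess from about 0.3 of a woman to about 5 women per arm of 44, before dilution within ATC rows. This rests on the conditional reading of 5.6.3, on use before consent being balanced by randomisation, and on prior use being unrelated to which women have elevations. The table is descriptive, so the co-primary analyses, the error control and the sample size are untouched.

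**What to change.** In SAP 6.4 and 7.2.4, limit the by-arm previous-medication summary to medicines with at least one dose on or after the date of informed consent and before first study drug. Every woman then has the same look-back.

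Present the liver-triggered 90-day records in a separate listing covering every woman for whom they were collected. The suspected-injury listing in SAP 7.5.2.1 is too narrow for this. The trigger in 5.6.3 has no threshold, whereas suspected injury (Protocol 9.14.2) needs more than 8 x ULN, more than 5 x ULN for over 2 weeks, or more than 3 x ULN with a bilirubin, INR, symptom or eosinophil criterion. A woman with an isolated, asymptomatic rise above 3 x ULN has an event of special interest, yet her look-back would appear nowhere.

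The cost is one SAP sentence, one date filter and one listing. No new data are collected and no liver information is lost. The change can be made before the SAP is finalised, which SAP section 1 places before hard lock and unblinding.
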